Design: A Phase III, randomised, triple-blind, placebo-controlled, parallel-group multicentre trial of vitamin D3 supplementation. Overall, 323 (of the target of 865) children aged 1-5 years, with asthma triggered by URTI, ≥ 4 URTIs in past year (or ≥ 2 URTIs in past 12 months if pertaining to the pandemic period) and ≥ 1 OCS in the past 6 months (12 months since February 2022) were recruited in 9 or more Canadian centers over a 7-year period in this high-intensity 7-month protocol. Year-round, children were randomly assigned to one of the two following study arms: (1) Intervention—two oral boluses of 100,000 IU vitamin D3 (3.5 months apart) with 400 IU daily vitamin D3 or (2) Control—identical placebo boluses with daily placebo dose.

Research question: Can vitamin D3 supplementation decrease the number of asthma exacerbations per child requiring rescue OCS (predominantly physician-initiated) vs placebo?

Randomisation was implemented through the Applied Clinical Research Unit (ACRU), at the CHUSJ, under the direction of the study statistician, [name]. A computer-generated random list was utilized, with randomisation stratified by site to ensure balanced allocation across different locations. Children were allocated to either the vitamin D3 or placebo group in a 1:1 ratio using a permuted block randomisation method, which enhanced allocation concealment. Group allocation codes for each site were securely stored with restricted access by the Central Pharmacy (CHUSJ) and the independent biostatistician. The active vitamin D3 and placebo preparations, provided by the manufacturer Europharm, were identical in appearance and taste, ensuring blinding. The allocated treatment numbers were forwarded to site pharmacies, which prepared the bolus in coded syringes and the coded bottles containing the daily dose and dispensed the study drugs in masked kits to maintain the integrity of the randomisation process.

Analysis objectives

The primary objective of this analysis is to evaluate whether vitamin D3 supplementation leads to a 25% relative reduction in the mean number of exacerbations requiring oral corticosteroids (OCS) per child over a 7-month period compared to placebo. We hypothesized that the number of OCS per child would approximately follow a Poisson distribution.

The secondary objectives are to assess differences between the treatment groups in:

- Mean number and type of laboratory-confirmed respiratory infections during asthma exacerbations.

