- Age 1-5 years
- Physician-diagnosed asthma (as per the 2015 Canadian Position Paper on the diagnosis of preschool asthma)
- ≥ 1 asthma exacerbation requiring rescue oral corticosteroids (OCS) in the past 6 months or ≥ 2 in the past 12 months from 2018 until 2020; then ≥ 1 asthma exacerbation requiring rescue oral corticosteroids (OCS) in the past 12 months, starting from the fall of 2020 (pandemic) onwards (as documented by pharmacy/medical records)
- ≥ 4 upper respiratory tract infections (URTIs) in the past 12 months (as per parental report) or ≥ 2 URTIs in past 12 months, starting from the fall of 2020 (pandemic) onwards
- URTIs as the main asthma trigger (as per parental report).

The inclusion criteria target a high-mordidity population, at risk of consequences from asthma exacerbations, ensuring they are the most likely to benefit from the treatment.

Exclusion criteria:

- Intake > 400 IU/day of vitamin D3 supplements or fish oil in the past 3 months
- Intention to use > 400 IU/day of vitamin D3 supplements or fish oil in the fall and winter
- Extreme prematurity (< 28 -week gestation)
- No vitamin D supplementation (if breast-fed in the last 6 months)
- Vitamin D restrictive diets, that is, minimal intake of vitamin D fortified milk (< 250 mL/day for 1-3 years or < 375 mL/day for 4-6 years) AND no other (or < 200 IU/day) vitamin D supplement
- Recent immigrants from regions at high risk of rickets (in the past 12 months)
- Recent refugees (in the past 12 months)
- Undernourished children
- Other chronic respiratory disease (e.g. Cystic fibrosis, Bronchopulmonary dysplasia) or chronic kidney, gastrointestinal, endocrinological or cardiac diseases, or sickle cell anemia
- History of bone disorder disease (e.g. rickets, osteomalacia)
- Intake of oral anti-epileptic, diuretic or anti-fungal medications
- Anticipated difficulty with follow-up or with adherence to the intervention or the procedures.

These criteria exclude participants prone to vitamin D deficiency, which could lead to hypocalcemia during vitamin D supplementation. They also exclude children already taking or planning to take over 400 IU/day of vitamin D, to prevent dilution of the treatment effect. Additionally, conditions or circumstances that could interfere with vitamin D metabolism or study follow-up are excluded to ensure reliable results.

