information on the coding and definitions for secondary outcome variables is provided in appendix 3. Each of these will be considered as binary variables separating participants into two groups for analysis as described below.

Planned subgroup analyses

In this study, seven baseline variables are *a priori* hypothesized to be potential effect modifiers:

- Baseline 25OHD serum level dichotomized (<75 vs. ≥ 75 nmol/L)
- Atopy (specific multiallergen IgE ≤ 0.35 or > 0.35 kUa/L),
- Asthma phenotype (viral-induced vs. multi-trigger),
- ICS therapy (pre-emptive vs. daily),
- Body mass index (< 85%ile vs. ≥ 85 %ile)
- Biological sex assigned at birth (male/female)
- Skin color (6 categories of Fitzpatrick scale, dichotomized for analysis as 1, 2 or 3 vs 4, 5 or 6)

Subgroups to consider (ad hoc)

Three additional variables were added to the set of potential subgroups to consider. These variables were added to the analysis plan prior to the start of analysis, in light of recent scientific knowledge since the beginning of the study

- Type 2 high vs. Type 2 low inflammation (Phadiatop ≥ 0.35 kUa/L) OR Eosinophils ≥ 300 cells/ μ L vs. neither)
- Past morbidity (≤ 2 vs > 2 OCS in past year)
- Prescribed GINA 4 Step-therapy at index visit (dichotomized as Step 1-2-3 vs 4)

Safety outcomes

The urine calcium:creatinine ratio, as a marker of normal calcium metabolism, was the primary safety outcome to assess the individual safety profile. Urine samples to test for hypercalciuria were systematically collected for immediate on-site analysis at baseline, 3.5 and 7 months, and at 10 days after each bolus. Site- and age-specific reference values were used for interpretation locally. In case of an elevated urine calcium:creatinine ratio, a site endocrinologist/bone specialist, blinded to group allocation, interpreted results and, if necessary, requested further analysis (urine or blood samples). Serious and non-serious adverse health events were ascertained at each visit and phone call.

The proportion of children with ≥ 1 occurrence of clinically significant:

- Hypercalciuria, clinically significant hypercalcemia (> 2.63 mmol/L), documented in the Safety Markers eCRF and Adverse effects eCRF; Q 3.3.1 Serum Ca Value (mmol/L) [safmark_biomark_caval].
- Elevated serum 25OHD (> 250 nmol/L—measured at the CHUSJ; exceptionally, if measured as part of investigation of adverse events, it may be documented in safety markers eCRF and

- Adverse effects eCRF;

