- Serious and non-serious adverse health events ascertained at each visit by Adverse effect eCRF and Serious adverse effect eCRF (and Visit and Phone eCRF and Medical Examination eCRF).

Exploratory outcomes

Group difference in:

1. Change in gene expression levels in peripheral blood mononuclear cells (PBMC) in a subset of patients, analyzed using whole transcriptome analysis by next-generation sequencing (RNAseq or equivalent), in some patients (from CHUSJ and MCH) at 0, 10 days, and 3.5 months.
2. Change in monocytes and lymphocytes' response to infection, namely to bacterial and viral products as well as responsiveness to corticosteroids (in vitro studies), examined at 0, 10 days, and 3.5 months in a subgroup of children.
3. Potential signature of responders vs. non-responders to vitamin D in PBMC and in gene polymorphisms from DNA or by patient and treatment characteristics.
4. Change in serum and nasal metabolome
5. Change in blood cell composition (specifically eosinophils) over the 7-month study.
6. Change in serum osteocalcin, telopeptides C, and other markers of *bone metabolism*.
7. The distribution of specific respiratory pathogens and virus load detected by qPRC.
8. Change from baseline in preschool lung function (respiratory resistance), when available at the specific institutions, documented in cooperative patients aged ≥ 3 years to assess a potential impact of vitamin D3 on lung growth.

Statistical procedures

Description of study cohort and positivity checks:

To ensure a comprehensive understanding of our study population, we will provide detailed descriptions of the clinical variables measured at inclusion for each group, summarized in a baseline characteristics table. This will encompass key baseline characteristics such as serum 25OHD levels, ICS therapy (daily ICS vs. Preventive ICS), clinical asthma phenotype, sex, atopy status, body mass index, skin color, type 2 inflammation, OCS use in preceding 12 months, Step therapy. We will also document the proportion of missing data for each variable.

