- Mean duration of use of β 2-agonist was used during each cold/asthma flare-up reported verbally or documented on the validated written 'Asthma Flare-up Diary for Young Children' over the time frame of 7 months (with each means of recording considered as a separate outcome).
- Mean of out-of-pocket asthma related expenses per exacerbation
- The sum of the daily ADYC scores as a measure of the severity of asthma symptoms during exacerbations, completed daily by parents using the validated 17-item, each scored from 1 (best) to 7 (worst), Asthma Flare-Up Diary for Young Children symptoms (ADYC) and standardized over 7 days
- Mean intensity of β 2-agonist use reported on the diary as
 - Cumulative rescue bronchodilator use: \sum daily number of puffs from the first day until last day of use until last day of use, inclusively. Units [puffs/episode]
 - Average rescue bronchodilator score = Cumulative rescue bronchodilator use \div duration of use, units [average puffs/day]
- Mean parents' functional status during exacerbations per child
 - Reported as the mean ECAP score
 - Reported as Global functional status on a 7-point likert scale from 1-not at all, to 7-extremely

Primary Efficacy Analyses

A Poisson regression model, will be estimated, using an ITT approach, including only randomization group as a predictor and adjusting only for the stratification of randomization by clinical site. This model will be used to estimate the incidence rate ratio comparing the mean number of oral corticosteroids (OCS) per child during the 7-month follow-up by study group. If overdispersion is present, a negative binomial model will be used. If there are large variations in person-time an adjustment using an offset term will be made. Two sensitivity analysis are planned; 1) the incidence rate ratio will be stratified by the month of recruitment to explore the possibility of effect modification by seasonality and 2) the incidence rate ratio will be stratified by year of the pandemic (2000-2001) to assess the possibility of effect modification by exposure to the COVID-19 pandemic period. The original analysis plan included a fixed effect for each site. However, for sites with a very small number of recruited patients, these small sites may be grouped together.

Secondary outcome analyses

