Potential modification of the effect of study intervention with vitamin D on primary and secondary outcomes will be assessed using the addition of interaction terms to the regression models. If there is a significant effect of the intervention, we will consider there as evidence of potential effect modification if inclusion of the interaction improves the overall model fit (using AIC/BIC criteria or R squared metrics), and if the interaction term is significant at an alpha of 0.20 or lower.

Statistical software and versions

The statistical analyses will be conducted using R 4.3.1 on Rstudio Server 2023.03.0. The following R packages are likely to be used based on the analysis requirements: base, stats, MASS, glm2, car, dplyr, tidyr, ggplot2, mice, Amelia, boot, heemod, BCEA.

Ancillary studies:

The economic evaluation will use standard trial-based economic evaluation methods. The intention is to provide the expected value of the intervention cost versus health care and family cost of exacerbations, effectiveness, and cost-effectiveness ratio with uncertainty around such values in terms of credible intervals.

References:

[name] FM, Jensen ME, Mendelson MJ, Parkin PC, Desplats E, Zhang X, Platt R. Asthma Flare-up Diary for Young Children to monitor the severity of exacerbations. *J Allergy Clin Immunol.* 2016 Mar;137(3):744-9.e6. doi: 10.1016/j.jaci.2015.07.028. Epub 2015 Sep 2. PMID: 26341275.

GINA 2024:www.ginasthma.com with ICS Doses based on Canadian Thoracic Society 2021 Guideline

Yang CL, et al. 2021 Canadian Thoracic Society Guidelines. *Can J Resp Crit Care Sleep Med.* 2021:1-41

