In addition to prespecified subgroup variables, 3 new categories will be explored as *ad hoc* analysis, based on new hypotheses (arising after the beginning of the study) regarding potential modification of the effect of vitamin D on asthma related outcomes; they are mentioned post-hoc as they were voiced after the last protocol version and after considering the distribution of these variables in all randomized individuals; of note, there were added before any blinded analysis by group or after unblinding.

Type 2 inflammation

Subgroups: 2 categories, Type 2 High vs. Type 2 Low.

Objective: To assess if Type 2 inflammation affects the treatment outcomes.

Type 2 inflammation includes allergic asthma and eosinophilic asthma and is defined as:

Type 2 High: Atopy positive (Phadiatop ≥ 0.35 - POSITIVE) OR Eosinophils ≥ 300 cells/ μL

Type 2 Low: Atopy negative (Phadiatop < 0.35 - NEGATIVE) AND Eosinophils < 300 cells/ μL

Past Morbidity in previous 12 months

Past morbidity is defined as the number of OCS administered in 12 months prior randomization.

Subgroups: ≤ 2 vs > 2 OCS reported.

Objective: To examine if intensity of use of rescue OCS in the 12 months prior to index visit is associated with the response to vitamin D3 supplementation.

REDCap Codebook: Baseline Demographics CRF (baseline_demographics)

Variable: [bd1_4_nbr_ocs] 6.1 Episodes with oral corticosteroids (prescribed, served and/or administered) .

Values:

- 1 Unknown
- 2 0
- 3 1
- ...
- 21 19
- 22 20
- 23 more than 20

Prescribed GINA 4 Step-therapy at index visit

Subgroups: Step therapy, dichotomized as Step 1-2-3 vs 4, at baseline, based on the 2014 GINA report.

Objective: To assess if asthma severity (severe vs. non-severe) defined by the intensity of asthma maintenance therapy (daily inhaled corticosteroid therapy with/without adjunct therapy) and/or the intensity of therapy itself affects the efficacy of vitamin D3 in reducing asthma exacerbations.

Step therapy (defined by GINA 2024)

According to the updated Global Strategy for Asthma Management and Prevention (2024), for children of 5 years and younger.

Step	Daily Tx, children of 5 years and younger
STEP 1	No Rx
STEP 2	1.Low dose maintenance ICS OR 2.Daily LTRA (Montelukast)
STEP 3	1.Double low (moderate) dose maintenance ICS OR 2.Low dose ICS + LTRA 3. Low dose ICS + LABA (if age >=4 years) No other adjunct therapy (no LAMA)

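### The primary model adjusts for site only; adding the prior-12-month OCS count, already collected, is a cheap optional gain in precision if counts are overdispersed

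*SAP*

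**What the plan says.** The SAP (Primary Efficacy Analyses) specifies a Poisson regression by intention to treat, "including only randomization group as a predictor and adjusting only for the stratification of randomization by clinical site", with a switch to negative binomial if overdispersion is present. Covariates names site for adjustment and treats the other listed baseline variables, past morbidity among them, as potential effect modifiers.

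Appendix 3 states: "Past morbidity is defined as the number of OCS administered in 12 months prior randomization". The variable comes from the Baseline Demographics form and is coded as single counts from 0 to 20, plus categories for more than 20 and for unknown. It has two named uses:

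- The baseline table, as "OCS use in preceding 12 months" (Description of study cohort and positivity checks).
- An ad hoc subgroup cut at 2 or fewer against more than 2 courses. Effect modification "will be assessed using the addition of interaction terms to the regression models" (Subgroup Analyses).

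It may have two further uses. The imputation of missing values adjusts for baseline variables, and the positivity check models the probability of intervention given baseline variables. Neither section lists its variables.

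**The concern.** A baseline count of the same event as the endpoint is the natural prognostic covariate for a count outcome. On its eligibility rules, which include prior OCS courses, the SAP says: "The inclusion criteria target a high-mordidity population, at risk of consequences from asthma exacerbations". It also considers past OCS use important enough to test as an effect modifier. Yet the primary estimate does not use the variable, and the interaction models would bring it in only in dichotomised form.

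What is at stake is precision. Introduction, Design reports 323 children recruited of a target of 865. Where counts are overdispersed, a covariate that explains part of the between-child variation narrows the confidence interval without new data.

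**Working it through.** **Inputs from the SAP.** N = 323, target 865, 1:1 allocation, rate ratio 0.75 (25% reduction), final-look two-sided alpha 0.046946 (critical value about 1.987). The control mean m0, the dispersion k and the share f of between-child heterogeneity explained by the prior count are not given; all three are assumed below.

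**The plan's own figure.** The target of 865 cannot be reproduced from the SAP, because power and control mean are absent. With N per arm = (1/m0 + 1/(0.75 m0) + 2k)(z_a + z_b)²/ln(0.75)² at alpha 0.05, several inputs come close: 886 (Poisson, 80% power, mean 0.5); 856 (Poisson, 90% power, mean 0.75, 7.5% loss); 890 (k = 1, 80% power, mean 1, 7.5% loss). They do not settle m0 or k.

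**Analytic effect of adjustment.** V = [(1/m0 + k) + (1/m1 + k)]/161.5 with m1 = 0.75 m0. After adjustment, k becomes k(1 − f). Equivalent extra children = 323 × (V/V_adj − 1).

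For m0 = 1.0, k = 0.5, f = 0.2:
- V = (1 + 1.3333 + 1.0)/161.5 = 3.3333/161.5
- V_adj = (1 + 1.3333 + 0.8)/161.5 = 3.1333/161.5
- fall = 0.2/3.3333 = 6.0%
- extra children = 323 × 0.2/3.1333 = 20.6

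| m0 | k | f | Fall in variance | Equivalent extra children | Power |
|---|---|---|---|---|---|
| 1.0 | 0.5 | 0.2 | 6.0% | 21 | 50.6% to 53.1% |
| 1.0 | 0.5 | 0.1 | 3.0% | 10 | not computed |
| 0.7 | 0.5 | 0.2 | 4.6% | 16 | 40.9% to 42.5% |
| 0.5 | 0.5 | 0.2 | 3.5% | 12 | 32.6% to 33.6% |
| any | 0 | any | 0% | 0 | unchanged |

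Over m0 0.5 to 1.5, k 0.25 to 1 and f 0.1 to 0.3, the fall runs from 1.0% to 16.9%.

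**How large f might be.** In a large-sample check (mean 0.5 to 1.0, k 0.25 to 1), the prior count explained 4 to 16% of heterogeneity if half of it persists from the prior year, for a gain of 0.3 to 4.4%. If all persists, it explained 15 to 57%, for a gain of 1.1 to 16.7%. So f = 0.2 lies above the half-persistence range.

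**Simulation 1** (N = 323, 3,000 trials per cell, 8 site groups, log(1 + count) capped at 6, six zero counts, 5% unknown; k = 0.5 where overdispersed):
- Half persists: model variance falls 2.2% at mean 1.0 (power 53.7% to 54.6%) and 1.0% at mean 0.6 (37.4% to 38.2%). At mean 0.6 the empirical variance does not fall (+0.2%).
- All persists, mean 1.0: model variance falls 8.1% (power 53.9% to 58.8%).
- Poisson: model variance rises 0.5% (power 65.2% to 65.0%).
- Rejection under no effect, nominal 0.0469: 0.042 to 0.055 site-only, 0.045 to 0.057 adjusted.
- With a constant effect, the average rate ratio moves by at most 0.002.

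**Simulation 2** (N = 323, 300 replicates per cell, 5 sites, log count, prior-year mean 2 truncated at 1 or more, control mean 0.75 or 1.25, k = 0, 0.5 or 1). Ratio of adjusted to unadjusted variance:
- k = 0: 1.00.
- Correlation 0.5 between prior and trial-period propensity: 0.95 to 0.98, a gain of about 2 to 5%. Power changes are within Monte Carlo error (about 3 points).
- Correlation 1: 0.78 to 0.93, a gain of about 7 to 22%. The best cell is equivalent to 323/0.778 = 415 children.

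**If the prior count modifies the effect.** Large-sample fits (control mean 1, frailty variance 0.5) with rate ratios of 0.9 at 2 or fewer courses and 0.65 above gave 0.759 unadjusted and 0.768 adjusted. With 0.6 and 1.0 they gave 0.827 and 0.807. A second set of fits with effect modification gave 0.759 and 0.765, and 0.834 and 0.821. The differences are 0.006 to 0.020.

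**The case against.** The strongest reply is that nothing here is wrong. The plan chooses site-only adjustment explicitly and repeats it for the secondary outcomes, and that model is valid. This stands, and it is why the point is optional. A reader might infer that omitting the count biases the primary estimate or is an error in the plan; the document does not support either.

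The gain may also be nil. On the primary endpoint the SAP says: "We hypothesized that the number of OCS per child would approximately follow a Poisson distribution". If so, adjustment costs a little and returns nothing. Requiring at least one prior OCS course truncates the covariate and does not show that it is prognostic among those selected. The look-back rule was also relaxed during the pandemic. These points stand and favour the lower end of the range.

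A reader might infer that the count is used nowhere else. That is not established, because the imputation and positivity models do not list their variables.

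Finally, a late change to a primary model invites suspicion. Past morbidity was named after the last protocol version, once its distribution in all randomized children had been considered. But of the ad hoc subgroup variables the SAP says: "These variables were added to the analysis plan prior to the start of analysis", and Appendix 3 places this before any analysis by group. A blind addition to the model would be made on the same footing. The objection becomes decisive only if the data are already unblinded.

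**Conclusion.** This is a cheap improvement, not a correction. The expected change in the variance of the log rate ratio is:

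- none, or about 0.5% lost, if counts are Poisson;
- about 1 to 5% lower if counts are overdispersed and propensity partly persists;
- roughly 7 to 22% lower only if it persists fully.

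Every figure rests on an assumed control mean, dispersion and prognostic strength. Overdispersion is necessary for a gain but not sufficient: the prior count must explain part of it.

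A reader might infer that adjustment repairs the recruitment shortfall. It does not. The shortfall is 865 − 323 = 542 children; the f = 0.2, mean 1.0 case is worth about 21 of them (4%), and the best simulated case reaches the equivalent of 415 children in all.

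Nor is the adjusted rate ratio the same quantity under all conditions. It keeps the same target if the effect is constant. If the prior count modifies the effect, which the SAP considers possible, the two estimates can differ by about 0.01 to 0.02.

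**What to change.** Before unblinding, add the prior-12-month OCS count to the primary Poisson or negative binomial model alongside site, and state:

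- one functional form that is defined at zero, for example log(1 + count) with a stated cap, which also deals with the category above 20;
- the recoding, since the stored codes in Appendix 3 run two above the count and code 1 means unknown;
- a rule for unknown values that is blind to arm, such as a missing category or single imputation from baseline data;
- the site-only model as a sensitivity analysis.

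If the data are already unblinded, keep site-only as primary and label the adjusted model supportive.

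The cost is SAP wording, one or a few extra parameters and the missing-value rule. No new data are needed. The risk is the very small loss of precision if counts turn out close to Poisson.

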Source documents anonymized and retained in the patient study binder include pharmacy records, medical records, relevant information from Dossier de Santé du Québec (DSQ) or similar databases if obtained by the treating physician, laboratory results, and pulmonary function test results.

The data is organized in a tabular format within REDCap, with each row representing a participant observation (one row per event per person) and each column representing a specific data field. Data exports are available in CSV, Excel, and XML formats. The data fields include various types such as text, number, date, and multiple choice. The data dictionary is accessible within the REDCap project and provides detailed descriptions of each data field, including field names, types and allowed values.

Samples and Laboratory Databases:

- Biobank log (xlsx file, managed by the study Coordination Centre)
- CHUSJ Lab results for urine and blood (xlsx file, uploaded directly to OwnCloud),
- McMaster University Lab results for nasal swabs (xlsx file, uploaded directly to OwnCloud),
- Oscillometry results (data exported from the Tremoflo software, managed by the study Coordination Centre)

The detailed description of samples/data transfer and storage is described in the Data Management Plan.

Analysis sets/Populations/Subgroups

The target population for this study includes children aged 1-5 years with physician-diagnosed asthma, who have experienced recurrent, moderate/severe viral-induced exacerbations in the

preceding year. These children were treated with daily or pre-emptive inhaled corticosteroids (ICS) alone or with adjunct therapy as the standard of care from randomization onwards, and were randomized to receive either vitamin D3 supplementation or placebo. The sampling frame consists of potentially eligible children seen in one of the 9 participating pediatric institutions. Recruitment occurred in the fall over 3 months (Sept to Nov) for 1 year (2018), over 5 months per year (from Sept to January) for 3 years (2019-2021), than year-round for another 3 years (2022-2024), over a total period of 7 years. The analysis sample (n=323) includes all randomized participants regardless of adherence to the intervention protocol or whether they completed the study (intention-to-treat analysis). Of note, the consent form allowed data collection of the primary outcome until 7 months post-randomization, even in case of withdrawals or loss to follow-up.

Inclusion criteria:

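### Seasonal effect modification is to be explored through month-of-recruitment rate ratios in 323 children, which gives low power and is prone to chance extremes; one treatment-by-season term would serve better

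*SAP*

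**What the plan says.** Under Primary Efficacy Analyses, the SAP plans a Poisson model adjusted for site, with a negative binomial fallback, and then two sensitivity analyses. In the first, "the incidence rate ratio will be stratified by the month of recruitment to explore the possibility of effect modification by seasonality". That section does not combine months into seasons, name a test of heterogeneity or say how the monthly ratios are to be read.

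The sample is fixed: "Overall, 323 (of the target of 865) children aged 1-5 years" were recruited, and "The analysis sample (n=323) includes all randomized participants".

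The months were not equally open. According to Analysis sets/Populations/Subgroups, "Recruitment occurred in the fall over 3 months (Sept to Nov) for 1 year (2018", then "over 5 months per year (from Sept to January) for 3 years (2019-2021), than year-round for another 3 years (2022-2024".

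The Subgroup Analyses section plans to assess effect modification by adding interaction terms to the regression models. Season is not among the seven planned or three ad hoc subgroup variables, and the seasonal analysis does not refer to that section.

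**The concern.** Season is a plausible modifier on the SAP's own account. The Introduction places exacerbations mainly in the fall and winter, and says that vitamin D insufficiency rises further in winter. Splitting 323 children by month leaves small strata and up to twelve ratios, with no stated way to judge whether they differ by more than chance.

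Month of recruitment is also too fine a scale for a slowly varying exposure. Follow-up lasts 7 months, so children recruited in adjacent months share about six of their seven months of follow-up. Twelve strata spend 11 degrees of freedom on something that one or two could describe.

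What is at stake is the usefulness of this exploration. A month with a halved or doubled rate could be read as a seasonal signal, while real modification could be missed.

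**Working it through.** **Plan's own figure.** The SAP states no precision or power for this analysis. Its target of 865 cannot be reproduced, because it gives neither the power nor a control event rate. The objective is a "25% relative reduction in the mean number of exacerbations requiring oral corticosteroids (OCS) per child over a 7-month period", and "We hypothesized that the number of OCS per child would approximately follow a Poisson distribution". Solving backwards with n per arm = (1.96 + z_β)² × (1/λ₀ + 1/(0.75 λ₀)) / (ln 0.75)², and 432.5 per arm (400 with 92.5% retention):

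- 80% power: λ₀ = 0.51 to 0.55.
- 90% power: λ₀ = 0.69 to 0.74.

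The working range below, λ = 0.6 to 0.9 courses per child over 7 months, is an assumption. Dispersion k is taken as 0 (Poisson) or 0.5 (negative binomial), also assumed.

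**Children per month.** The average is 323/12 = 26.9, or 13.46 per arm. From the stated windows, September to November were open in 7 years, December and January in 6, and February to August in 3. That makes 3×7 + 2×6 + 7×3 = 54 open month-slots. If accrual were proportional to slots (an assumption):

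- September to November: 323×7/54 ≈ 42 each.
- December and January: 323×6/54 ≈ 36 each.
- February to August: 323×3/54 ≈ 18 each.

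This pools the same calendar month across years, which is the favourable reading.

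**Precision of one monthly ratio.** With no true effect, SE(log IRR) = √((2/λ + 2k)/n per arm), and the 95% CI factor is exp(1.96 × SE).

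| Stratum | n per arm | k | factor, λ = 0.6 | factor, λ = 0.9 |
|---|---|---|---|---|
| Equal months | 13.46 | 0 | 2.65 | 2.22 |
| Equal months | 13.46 | 0.5 | 3.04 | 2.61 |
| February–August month | 8.97 | 0 | 3.30 | 2.65 |
| February–August month | 8.97 | 0.5 | 3.90 | 3.24 |

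**Chance extremes with no true effect.** The probability that one month lies outside 0.5 to 2 is p = 2 × (1 − Φ(ln 2 / SE)). For twelve equal months the chance of at least one is 1 − (1 − p)¹².

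- k = 0: λ = 0.6 gives SE 0.498, p = 0.164, chance 88%. λ = 0.9 gives SE 0.406, p = 0.088, chance 67%.
- k = 0.5: λ = 0.6 gives 95%, and λ = 0.9 gives 87%.
- Months filled as 42, 36 and 18: about 78 to 92% (k = 0) and 91 to 97% (k = 0.5).

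The overall range is 67 to 97%. In simulation at λ = 2.0 with equal months and k = 0, it falls to about 17%. Over λ = 0.5 to 2.0, the chance of at least one month with nominal p < 0.05 and no true effect is 21 to 43%.

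**Power to see real modification.** The assumptions are λ₀ from 0.5 to 2.0, k = 0 or 0.5, two-sided 5%, and a true IRR that differs between September–February and March–August recruitment.

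| Analysis | IRR 0.5 vs 1.0 | IRR 0.60 vs 0.94 |
|---|---|---|
| 12 months, 11 df | 16–76% | 9–36% |
| One-harmonic term, 2 df | 28–90% | 14–56% |
| Correctly chosen two-season contrast, 1 df | 42–98% | 21–75% |

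The SAP does not specify the 11-df test.

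**Precision of the alternative.** With two equal halves (80.75 per arm in each), each season's own ratio has a CI factor of 1.38 to 1.49 (k = 0). The interaction is the ratio of the two, so its variance is doubled. Its CI factor is 1.58 to 1.76 (k = 0) and 1.74 to 1.90 (k = 0.5).

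**The case against.** The strongest reply is that little hangs on this. It is one of two sensitivity analyses, is described as exploring a possibility, and drives no decision. The SAP claims no power for it and sets no rule that singles out a month. That stands, and it limits the weight of the point.

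It can also be argued that an interaction approach already exists, because Subgroup Analyses speaks generally of effect modification on primary and secondary outcomes. A reader might therefore reject any suggestion that the SAP has no interaction method, and would be right. What remains is that season is not on the subgroup list and the seasonal analysis does not point to that rule, so whether it applies is unclear.

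A reader might infer that monthly ratios cannot detect seasonality at all, or that spurious large effects are all but certain. The documents support neither. An 11-df test would have some power for a large modification. The chance of an extreme month depends on an event rate that the SAP does not give, and on a cut-off of 2 or 0.5 chosen here for point estimates. Nominally significant months would be much less common.

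Finally, an obvious repair, contrasting September–January with February–August recruits, is poor. An August recruit is followed through fall and winter, and a January recruit mostly through spring and summer, so both land on the wrong side. February to August was open only in 2022–2024, after the entry criteria had been relaxed, so that contrast also mixes season with calendar period and eligibility.

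**Conclusion.** The point holds as a minor improvement. Stratifying by recruitment month spreads 323 children over strata averaging 27, and the section fixes no grouping and no linked test. At an assumed 0.6 to 0.9 courses per child, monthly CIs span a factor of about 2.2 to 3.0 either side (equal months), and up to 3.9 in the sparsest months with dispersion 0.5. At least one ratio beyond 2 or 0.5 arises by chance in about 67 to 97% of trials with no true effect. These figures rest on the assumed event rate, dispersion and accrual pattern; higher event rates lower them. They ignore site adjustment, which would cost some further precision.

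Nothing here touches the primary ITT estimate or its conclusion, and it should not be read that way.

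**What to change.** In Primary Efficacy Analyses, replace the monthly stratification with one prespecified treatment-by-season interaction in the primary model, including the season main effect. Define season by exposure during follow-up rather than by the recruitment windows. Two options are the share of the scheduled 7 months after randomisation that falls in fall/winter (with those calendar months named in advance), or a one-harmonic term in randomisation date. Both are fixed at randomisation. Report the interaction estimate with its 95% CI and p-value, and state whether the 0.20 threshold under Subgroup Analyses applies to it. Monthly ratios may stay as a descriptive display.

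The cost is a few lines of SAP wording and no new data. Month-level detail loses prominence. Power for mild modification stays modest, with an interaction CI factor of about 1.6 to 1.9 for a two-group split, so a null result should not be read as absence of seasonality.
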